# 6.4.2 Allowed study drug adjustments

For patients who cannot tolerate the administration schedule specified in the protocol, dose adjustments are allowed so that the patient may continue to receive the study drug.

The study drug for this study will be pasireotide LAR 60 mg given every  $28 \pm 3$  days for 6 months, during the main study period. In case of tolerability issues (see Table 6-2), the pasireotide LAR dose may be decreased to 40 mg in the next scheduled injection. However, patients unable to tolerate the minimum dose of 40 mg will be discontinued from the study.

All dose changes must be recorded in the Dose Administration Record eCRF.

During the Extension Phase, if a patient receives 40 mg due to tolerability issues and such issues are resolved, there may be a dose escalation to 60 mg, at the physician's discretion. If the adverse event reoccurs, the dose will be decreased to 40 mg and the patient will maintain this dose.

Table 6-2 Guideline for treatment of patients experiencing adverse events

Adverse event	Action
CTC Grade ≤ 2 AEs	No drug adjustment
CTC Grade ≥ 3 AEs evaluated as related to the study drug	Decrease intramuscular pasireotide LAR dose to 40 mg.
	If the AE does not improve to grade ≤ 2 with the 40 mg dose, the patient will be withdrawn.

The guidance above must be used for all AEs, except for changes in blood glucose and QTc and for liver safety monitoring. Blood glucose changes must be followed as described on Section 7.5.2.1. Changes in QTc interval must be followed as described on Section 7.5.2.2. Refer to Section 7.5.2.3 for liver safety monitoring.

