# 10.5.1 Efficacy variables and analysis

The secondary efficacy endpoints are described on section 3.3.2.

The changes in mean and percent tumor volume variation from baseline to Weeks 4, 12, and 24 will be presented together with the 90% confidence interval (90% CI). If the data are in a non-normal distribution, median CI will also be generated. The incidence rate of patients with tumor volume decrease  $\geq$  20% and its exact CI will be reported on weeks 4 and 12.

Summary of the statistical analyses will be provided for each disease-related symptom (headache, visual disorders, fatigue, decreased libido, and specific symptoms for men and women) on each visit. Changes in baseline scores will be summarized on each visit for all symptoms.

The time to response, defined as the time from the first injection to the first evaluation in which a patient reaches a tumor volume decrease of at least  $\geq 20\%$ , will be listed for all patients. If a patient did not reach tumor response, the period of his/her last evaluation will be used as a cutoff period. For responsive patients, average time to response will be summarized.

Additionally, logistic and cox regression models may be used to explore the association between baseline characteristics and tumor response and time to tumor response. These analyses will be specified in the report analysis plan (RAP).

The frequency and percentage of patients experiencing improvement of symptoms related to tumor compression, pituitary hormone dysfunction, normalization of the alpha subunit level, will be presented for each symptom at each period with the associated exact 90% CI.

The incidence rates of pituitary hormone dysfunction, the normalization of alpha subunit levels, and the proportion of patients with a 50% decrease in the alpha subunit level, together with the exact 90% CI will be reported at baseline and on weeks 4, 12, and 24. The alpha subunit level analyses will be performed again with the population set according to protocol and for the subgroup of patients with increased alpha subunit levels at baseline.

Hormone profiles, alpha subunit levels, in each period in terms of frequency (N), mean, standard deviation, median, minimum, and maximum.

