5.5.1 Efficacy variables and analysis

The secondary efficacy endpoints are described in section 1.2.1.

The mean and percent change in tumor volume from baseline to Week 4, 12 and 24 will be presented along with the 90% confidence interval (CI). If data is found to be skewed, CIs for median will also be generated. Incidence rates for patients with \geq 20% reduction in tumor volume and its exact CI will be reported at Week 4 and 12.

Summary statistics will be provided for each disease related symptoms (headaches, visual disturbance, fatigue, symptoms specific to man and woman) at each visits. Change from baseline scores will be also summarized at each visit for all symptoms.

Time to response, defined as time from the first injection to first evaluation where patient achieve tumor volume reduction of at least \geq 20%, will be listed for all patients. If a patient has not achieved tumor response, the time of last assessment will be indicated as censoring time.

Kaplan-Meier analysis will be performed for time to response aiming to compute the median time to response and corresponding 95% confidence interval. Cox regression exploratory analysis will be used to estimate the hazard ratio with corresponding 95% confidence intervals for time to tumor volume reduction of at least \geq 20% as a function of baseline characteristics (duration of disease, dose at V2, dose reduction, visual field (abnormal/normal), and α subunit at V1).

Logistic regression will be performed to explore association between baseline characteristics and tumor response.

Frequency and percentage of patients who present improvement of symptoms related to tumor compression, pituitary hormonal dysfunction, alpha subunit level normalization, will be presented for each symptom at each time point with associated exact 95% CI.

Incidence rates of pituitary hormonal dysfunction, normalization of alpha subunit level and proportion of patients with 50% reduction in alpha subunit level along with its exact 95% CI will be reported at baseline, Week 4, 12 and 24. Analyses for alpha subunit level will be repeated with per protocol population set and for the subgroup of patients with elevated alpha subunit level at baseline.

Hormone profiles, alpha subunit levels and will be summarized at each time point in terms of frequency (N), mean, standard-deviation, median, minimum, and maximum.

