Reduction of							
tumor							
volume ^{b)} , n (%)							
Yes							
No							
≥20% tumor							
volume							
reduction ^{c)} , n							
(%)							
Yes							
No			-		-		-
Total			-		-		-
≥20% tumor							
volume							
reduction using							
LOCF method, n							
(%)							
Yes			-		-		
No			-		-		
Total							

95%CI: 95% confidence interval.

a) The difference between visit i and V1.

b) For reduction='yes' will be considered all patients who obtained 'volume in visit i – volume in V1' >0.
c) For reduction ≥20%='yes' will be considered all patients who obtained 'Percentage change in volume at visit i' ≥20.

Table 8 – Time to response – FAS population

	Total		
	(n=xx)		
	Statistics	95% CI	
Time to response			
N			
Censored			
Events (Reduction ≥20% in tumor volume)			
Mean			
Median			
25 th Percentile			
75 th Percentile			
Range			

Cl_{95%}: 95% confidence interval.

Time between first administration and first date of reduction ≥20% in tumor volume.

Figure 3 – Kaplan-Meier curve for time to response – FAS population

Table 9 – Time to response versus baseline characteristics – FAS population

Time to response a)	Total					
	n=(xx) Statistics	Cl _{95%}	Statistics	Cl _{95%}		
	Statistics	C13576	Statistics	G19376		
Visual field at baseline	Normal		Abnormal			
Fime to response ^{a)}						
N						
Censored						
Events (progression or death)						
Mean						
Median						
25 th Percentile						
75 th Percentile						
Range						
Hazard ratio ^{b)}						
p-value						
Dose at V2	60 mg		40mg			
Time to response a)	oo mg		TVIIIS			
N						
Censored						
Events (progression or death)						
Mean						
Median						
25 th Percentile						
75 th Percentile						
Range						
Hazard ratio b)						
p-value						
•						
Dose reduction before response	Yes		No			
Time to response a)						
Time to response ^{a)} N Censored						
Time to response ^{a)} N						
Time to response ^{a)} N Censored Events (progression or death) Mean						
N Censored Events (progression or death) Mean Median						
N Censored Events (progression or death) Mean Median 25 th Percentile						
N Censored Events (progression or death) Mean Median 25 th Percentile 75 th Percentile						
N Censored Events (progression or death) Mean Median 25 th Percentile						
N Censored Events (progression or death) Mean Median 25 th Percentile 75 th Percentile						
N Censored Events (progression or death) Mean Median 25 th Percentile 75 th Percentile Range						

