N Censored Events (progression or death) Mean Median 25 th Percentile 75 th Percentile Range Hazard ratio ^{b)} p-value						
N Censored Events (progression or death) Mean Median 25 th Percentile 75 th Percentile Range Hazard ratio ^{b)} p-value						
Time to response a) N Censored Events (progression or death) Mean Median 25 th Percentile 75 th Percentile Range Hazard ratio b) p-value Duration of disease (years)						
N Censored Events (progression or death) Mean Median 25 th Percentile 75 th Percentile Range Hazard ratio ^{b)} p-value Duration of disease (years) Hazard ratio ^{b)}						
N Censored Events (progression or death) Mean Median 25 th Percentile 75 th Percentile Range Hazard ratio ^{b)} p-value Duration of disease (years) Hazard ratio ^{b)}						
Time to response a) N Censored Events (progression or death) Mean Median 25 th Percentile 75 th Percentile Range Hazard ratio b) p-value Duration of disease (years) Hazard ratio b)						
Time to response a) N Censored Events (progression or death) Mean Median 25 th Percentile 75 th Percentile Range Hazard ratio b) p-value Duration of disease (years) Hazard ratio b) p-value						
Time to response a) N Censored Events (progression or death) Mean Median 25 th Percentile 75 th Percentile Range Hazard ratio b) p-value Duration of disease (years) Hazard ratio b)						

Cl_{95%}: 95% confidence interval.

Time between first administration and first date of reduction ≥20% in tumor volume.

a) Kaplan-Meier estimates. b) Cox regression estimates.

Table 10 – Disease-related symptoms – FAS population

	Total									
	(n=xx) V1	V2	V3	V4	V5	V6	V7	V8	V9	V10
Headache ^{a)} , n (%)										
Absent										
Mild										
Moderate										
Severe										
Very severe										
Total										
Improved, n (%)										
Yes										
95%CI										
No										
Total										
Visual disturbances a),	n									
(%)										
Absent										
Mild										
Moderate										
Severe										
Very severe										
Total										
Total										
Improved, n (%)										
Yes										
95%CI										
No										
Total										

Table 10 (Cont.) – Disease-related symptoms – FAS population

	Total									
	(n=xx)									
	V1	V2	V3	V4	V5	V6	V7	V8	V9	V10
Fatigue ^{a)} , n (%)										
Absent										
Mild										
Moderate										
Severe										
Very severe										
Total										
Improved, n (%)										
Yes										
95%CI										
No										
Total										
Erectile dysfunction	1 b)									

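### The exploratory Cox model for time to response treats post-baseline dose reduction as a baseline factor, includes a Visit 2 dose that does not vary, and Table 9 names the wrong event

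*SAP*

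**What the plan says.** Protocol 10.5.1 allowed that "logistic and cox regression models may be used to explore the association between baseline characteristics and tumor response and time to tumor response", with details left to the analysis plan. SAP 5.5.1 supplies them: a Cox model with 95% confidence intervals for time to a volume reduction of at least 20%, "as a function of baseline characteristics (duration of disease, dose at V2, dose reduction, visual field (abnormal/normal), and α subunit at V1". It adds, without naming covariates, that "Logistic regression will be performed to explore association between baseline characteristics and tumor response".

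Table 9 in SAP Appendix 1 gives the output. The row "Dose reduction before response" has Yes and No columns, each with Kaplan-Meier estimates, plus a hazard ratio and p-value. Another row compares 60 mg with 40 mg at Visit 2. The event line in these blocks reads "Events (progression or death". The table's footnote defines the time variable as "Time between first administration and first date of reduction ≥20% in tumor volume", and Table 8, for the same endpoint, has "Events (Reduction ≥20% in tumor volume".

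On dosing, Protocol 6.3 and 6.4 give every patient 60 mg at Visit 2. Protocol 6.4.2 says that, for tolerability, "the pasireotide LAR dose may be decreased to 40 mg in the next scheduled injection".

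**The concern.** A patient's dose-reduction status is unknown at first injection, where the clock starts. Under Table 9's grouping, a responder counts as Yes only if the reduction came first, so that patient had to remain without a response until then. A non-responder reduced at any visit also counts as Yes. Anyone who responds early and would have been reduced later goes to No. The Yes group therefore carries response-free time that it was guaranteed by construction (immortal-time bias), which pushes the Yes-versus-No hazard ratio down relative to time-dependent coding. This happens only when reductions are still to come at the time of a response.

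A reader of Table 9 could take such a hazard ratio and p-value as evidence that patients whose dose was reduced respond less or later. Separately, a covariate with one value has no hazard ratio, and a line programmed literally as progression or death would count outcomes unlike the response being analysed.

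**Working it through.** **The plan's own figure.** SAP 5.6 gives a 58% chance of at least two responders among 19 at a 10% response rate: 1 − 0.9^19 − 19 × 0.1 × 0.9^18 = 1 − 0.1351 − 0.2852 = 0.580. It reproduces. Expected responders are 19 × 0.10 = 1.9.

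**Inputs from the documents.** Injections after Visit 2 are at Weeks 4, 8, 12, 16 and 20 (Protocol 7.3). Core-phase MRI is at Weeks 4, 12 and 24 (Protocol section 4), no more than 7 days before the visit (SAP Table A 1, footnote 16), so a scan precedes that visit's injection.

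**Assumptions.** The documents give no reduction rate or timing and no split of responses over the scans. I vary these, with no dropout. Response rates other than 10% are also assumed.

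**Method.** The expected hazard ratio θ solves the Breslow score equation

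Σ_k d1_k = Σ_k d_k × θY1_k / (θY1_k + Y0_k),

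where, at scan k, d is all responses, d1 is responses in Yes, and Y1 and Y0 are the Yes and No patients still at risk.

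**Worked case.** Assume 10% respond, equally over the three scans (0.0333 each), and 20% are reduced, evenly over the five injections and independently of response. The true θ is 1. The share of responders reduced before their scan is 0 at Week 4, 2/5 × 0.20 = 0.08 at Week 12, and 0.20 at Week 24. Yes responders total 0.0333 × (0 + 0.08 + 0.20) = 0.00933. Yes non-responders are 0.90 × 0.20 = 0.18. The Yes group is 0.1893.

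| Scan | Yes at risk / all at risk | Yes share of risk set | Yes share of responses |
|---|---|---|---|
| Week 4 | 0.1893 / 1.0000 | 18.9% | 0% |
| Week 12 | 0.1893 / 0.9667 | 19.6% | 8% |
| Week 24 | 0.1867 / 0.9333 | 20.0% | 20% |

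The equation requires the three fractions to sum to 0.28. At θ = 0.425 they are 0.090 + 0.094 + 0.096 = 0.280, so θ = 0.42. With time-dependent coding the reduced share of the risk set is 0%, 8% and 20%, equal to its share of responses, so θ = 1.00.

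**Range.** Over the responding/reduced pairs 10/20, 10/40, 20/30, 30/20 and 30/40%, with independence:

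| Responses at Weeks 4/12/24 (%) | Reductions even over Weeks 4–20 | Reductions only at Weeks 4–8 |
|---|---|---|
| equal thirds | 0.36–0.45 | 0.56–0.64 |
| 10/20/70 | 0.69–0.75 | 0.85–0.88 |
| 0/50/50 | 0.60–0.69 | 1.00 |
| 0/10/90 | 0.90–0.93 | 1.00 |
| 0/0/100 | 1.00 | 1.00 |

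Time-dependent coding gives 1.00 in every cell. A Week 12 response distorts the result only if some reductions fall at Week 12 or later.

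**Without independence.** With 20% responding, 30% reduced, even reductions and 10/20/70 timing: if reduction-prone patients respond 0.67 times as often, the fixed coding gives 0.49 against 0.66 time-dependent; if 1.5 times, 1.07 against 1.52. The grouping multiplies the hazard ratio by about 0.70 to 0.74, so it can hide a real association.

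**Estimability.** A finite hazard ratio needs a response in each group. With per-patient probabilities a (Yes response) and b (No response), the chance of failing this is (1 − a)^n + (1 − b)^n − (1 − a − b)^n. In the worked case with n = 19: 0.9907^19 + 0.9093^19 − 0.9^19 = 0.837 + 0.164 − 0.135 = 0.866. At 10% response, over 20–40% reduced and the equal, 10/20/70, 0/10/90 and 0/0/100 timings, the range is 63–87%.

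**Visit 2 dose and event label.** These need no arithmetic. Protocol 6.3 and 6.4 leave the 40 mg column at Visit 2 empty. Table 9's event line disagrees with its own footnote, with Table 8 and with section 5.5.1, which agree with one another.

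**The case against.** The SAP never states how non-responders are classified; that any reduction makes them Yes is inferred. A plain ever-reduced flag, which is all that 5.5.1 literally says, would give 1.00 under independence with full follow-up. That is correct, but Table 9 specifies reduction before response in fixed Yes/No columns, and the inferred rule is its natural reading. An ever-reduced flag would still not be a baseline characteristic.

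The protocol left the covariates to the analysis plan, and SAP section 7 declares this analysis as a clarification. There is also a listed secondary endpoint, if applicable, on response at 40 versus 60 mg, which explains the dose terms. Both points stand. They justify looking at dose, but they do not justify treating a later event as known at baseline.

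The size can be softened. Protocol section 4 says only that MRI is within 7 days of the visit. If scans follow the same-visit injection, equal timing gives 0.49–0.58 and 10/20/70 gives 0.76–0.82. SAP 5.4.3 expects an effect only after 24 weeks, which favours the smaller distortions. Time to response uses the full analysis set, so up to 23 patients could enter; the share without a finite hazard ratio is then 54–83%. These change the size but leave the mechanism.

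A 40 mg dose at Visit 2 could occur through a protocol deviation, and the event label is evidently a slip. Neither is a reason to leave the shell as it is.

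**Conclusion.** All three parts hold. Under Table 9's grouping the dose-reduction hazard ratio is biased downward whenever reductions are still to come at the time of a response. With independence, the value that should be 1.00 ranges from 0.36 to 1.00 across the scenarios. The late-response cases that the plan itself expects sit mostly at 0.69 to 1.00, and there is no bias if all responses come at Week 24. These sizes rest on assumed reduction rates, timings and response splits, no dropout, and scans read before the same-visit injection. The Visit 2 dose comparison is not estimable under the protocol, and the Table 9 event line is wrong.

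The importance is minor: the analysis is exploratory, the primary endpoint is untouched, and at a 10% response rate the hazard ratio would usually not exist.

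**What to change.** - Remove the Visit 2 dose from the model and from Table 9.
- Take dose reduction out of the baseline list in 5.5.1, and keep it out of the logistic model. Drop its fixed-group Kaplan-Meier estimates, hazard ratio and p-value.
- Report response by dose received descriptively. This also serves the 40 versus 60 mg endpoint; state that the comparison is descriptive because reductions follow adverse events.
- If a model is still wanted, use a time-dependent indicator (reduced before the given MRI, yes or no), name the reference group and call it optional.
- Relabel the Table 9 event line to match Table 8.

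This costs SAP wording and table-shell edits only, with no new data. The table loses a hazard ratio and p-value that would be very imprecise or not estimable with about two expected events.

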1.2 SECONDARY OBJECTIVES

- To assess the effect of pasireotide LAR on the mean change of tumor volume from baseline to Week 4, 12, 24, 48, 72 and 96.
- To assess the effect of pasireotide LAR on the percentage change of tumor volume from baseline to Week 4, 12, 24, 48, 72 and 96.
- To assess the effect of pasireotide LAR on the proportion of patients achieving tumor volume reduction of at least ≥20% after 4 and 12, 48, 72 and 96 weeks of treatment.
- To assess the effect of pasireotide LAR on the time to tumor response.
- To assess the effect of pasireotide LAR on the disease-related symptoms*
 - *Disease-related symptoms to be evaluated: headache, visual disturbances, fatigue, decreased libido, erectile dysfunction (for males only), irregular or stopped menses (for not post-menopausal female only).
- To evaluate the effect of pasireotide LAR on pituitary function at Weeks 4, 12, 24, 48, 72 and 96.
- To evaluate the effect of pasireotide LAR on alpha subunit levels at Weeks 4, 12, 24, 48, 72 and 96.
- To evaluate the overall safety and tolerability of pasireotide LAR.
- For extension phase: duration of response for patients considered responsive (*i.e.*, patients who achieved a tumor volume reduction of at least 20% with respect the initial tumor volume).
- To assess the percentage of patients that remain with tumor volume stable during the study.

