1.2.1 End-points for secondary objectives

The secondary variables are:

Mean change of tumor volume assessed by pituitary MRI from baseline to Week 4, 12, 24, 48, 72 and
 96.

- Percent change of tumor volume assessed by pituitary MRI from baseline to Week 4, 12, 24, 48, 72 and
 96.
- Proportion of patients achieving tumor volume reduction of at least ≥ 20% after 4, 12, 48, 72 and 96 weeks of treatment.
- Time to treatment response for treatment responders, defined as the time from the date of first injection to the first evaluation the patient achieves tumor volume reduction of at least >20%.
- Change from baseline to Week 4, 12, 24, 48, 72 and 96 in disease-related symptoms scores.
- Incidence of pituitary hormonal dysfunction at baseline and at Weeks 4, 12, 24, 48, 72 and 96.
- Proportion of patients achieving alpha subunit reduction of at least 50% at Weeks 4, 12, 24, 48, 72 and 96.
- Proportion of patients achieving normalization of alpha subunit at Weeks 4, 12, 24, 48, 72 and 96.
- Percentage of CTC (≥3) adverse events during treatment with pasireotide LAR.
- Percentage of patients with at least one adverse event with CTC grade ≥ 3.
- Incidence of all adverse events, incidence of laboratory abnormal values and summary of laboratory assessments.
- For extension phase: among patients who had been considered as responsive (*i.e.*, patients who achieved a reduction in tumor volume of at least 20% with respect to the initial tumor volume), assess the number and proportion of patients that remained responsive during the treatment period of extension phase (according to estimates by magnetic resonance at weeks 48, 72 and 96).
- To assess the percentage of patients who remained with tumor volume stable during the study, *i.e.* patients who maintained tumor volume with variation less than 20% with respect to the basal tumor volume (according to evaluations by magnetic resonance imaging at weeks 24, 48, 72 and 96).
- If applicable, assessing whether there was difference in response between patients using dose of 40 and 60 mg of pasireotide LAR.

2 Study design

This is a prospective, multicenter, open-label, single arm, phase II study to evaluate the efficacy and safety of pasireotide LAR in adult patients with NFPA.

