n(%)	. ,									
Yes										
No										
Total										
Improved, n (%)										
Yes										
95%CI										
No										
Total										

Table 10 (Cont.) – Disease-related symptoms – FAS population

	Total (n=xx)									
	V1	V2	V3	V4	V5	V6	V7	V8	V9	V10
Regular menses ^{c)} ,	n									
(%)										
Yes										
No										
Total										
mproved, n (%)										
Yes										
95%CI										
No										
Total										

a) For each symptom, it will considered as improvement if the severity reduce at least one point (eg. 'Severe' at v₁ and 'moderate' at v₁ will be considered as improvement in vi).

b) For patients who registered 'No' in V₁ and 'Yes' in v_i it will be considered as an improvement in v_i.

c) For patients who registered 'No' in V₁ and 'Yes' in v_i it will be considered as an improvement in v_i.

Table 11 (Cont.) – Alpha-subunit – FAS population

	Total (n=xx)					
	V1	V4	V7	95%CI	V10	95%CI
α subunit (ng/mL)						
N				-		-
Mean				-		-
Median				-		-
Standard Deviation				-		-
Minimum				-		-
Maximum				-		-
Normal				-		-
Abnormal				-		-
CS				-		-
NCS				-		-
Reduction of α subunit ≥50% ^{c)} , n (%)						
Yes						
No						
Total						

CS: Clinically significant; NCS: Not clinically significant. 95%CI: 95% confidence interval.

c) For reduction ≥50%='yes' will be considered all patients who obtained percentage change from baseline in α subunit at visit i' ≥50.

Table 13 – Visual field – FAS population

	Total							
	(n=xx)							
	V1	V2	V4	V5	V7	V8	V9	V10
Right eye								
Normal/abnormal, n (%)								
Normal								
Abnormal								
Mild								
Severe								
Total								
Findings, n (%)								
Upper right quadrantanopia								
Upper left quadrantanopia								
Lower right quadrantanopia								
Lower left quadrantanopia								
Temporal hemianopsia								
Nasal hemianopsia								
Other								
Evolutive information, n (%)								
Stable								
Improved								
Worsened								
Total								
Left eye								
Normal/abnormal, n (%)								
Normal								
Abnormal								
Mild								
Severe								
Total								
Findings, n (%)								
Upper right quadrantanopia								
Upper left quadrantanopia								
Lower right quadrantanopia								
Lower left quadrantanopia								
Temporal hemianopsia								
Nasal hemianopsia								
Other								

Table 13 (Cont.) – Visual field – FAS population

	Total (n=xx)							
	V1	V2	V4	V5	V7	V8	V 9	V10
Left eye Evolutive information, n (%) Stable Improved Worsened Total								

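### Alpha-subunit change is not planned to be summarised as a continuous within-patient change with an interval, so the size of a moderate fall is not estimated with precision

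*SAP*

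**What the plan says.** SAP 1.2 states the objective in terms of levels: "To evaluate the effect of pasireotide LAR on alpha subunit levels at Weeks 4, 12, 24, 48, 72 and 96". Two endpoints in SAP 1.2.1 carry it. One is "Proportion of patients achieving alpha subunit reduction of at least 50" percent, at the same weeks. The other is "Proportion of patients achieving normalization of alpha subunit at Weeks 4, 12, 24, 48, 72 and 96".

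SAP 5.5.1 analyses alpha subunit in three ways:

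- The two proportions are reported with exact intervals: "normalization of alpha subunit level and proportion of patients with 50% reduction in alpha subunit level along with its exact 95% CI". Protocol 10.5.1 plans the same with a 90% level: "the proportion of patients with a 50% decrease in the alpha subunit level, together with the exact 90% CI will be reported". SAP section 7 records the move to 95%.
- These analyses have a second population and a subgroup defined by the V1 value: "Analyses for alpha subunit level will be repeated with per protocol population set and for the subgroup of patients with elevated alpha subunit level at" (quote cut before its last word).
- The level itself is described visit by visit: "Hormone profiles, alpha subunit levels and will be summarized at each time point in terms of frequency (N), mean, standard-deviation, median, minimum, and maximum".

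Table 11 in SAP Appendix 1 has a row "Reduction of α subunit ≥50" percent, and its footnote defines that row from each patient's percentage change from baseline. In the same section 5.5.1, tumor volume gets mean change and percent change from baseline with a confidence interval, and symptom scores get change from baseline.

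**The concern.** The objective asks how far levels move. The planned outputs say how many patients crossed a line, and where the group stood at each visit. Neither gives the average change within patients together with its uncertainty. In a single-arm trial, each patient's own baseline is the only comparison available, so this is the natural estimate for a continuous marker.

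The SAP has to calculate the percentage change for every patient to apply the 50% rule, and then keeps only a yes or no. At stake is whether a moderate, fairly uniform fall can be reported as an estimate with an interval, or only as a small number of patients reaching 50%. Alpha subunit is treated differently here from tumor volume, and the documents give no reason.

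**Working it through.** **Inputs from the documents.** SAP 5.6 gives 19 evaluable patients, chosen without a power basis. SAP 5.5.1 gives 95% intervals for alpha subunit. Neither document gives an expected alpha-subunit change or an SD.

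**The plan's own figure.** The only operating characteristic stated is for the primary endpoint: the chance of two or more responders among 19 at a true rate of 10%. It is 1 − 0.9^19 − 19 × 0.1 × 0.9^18 = 1 − 0.1351 − 0.2852 = 0.580, which matches the stated 58%. There is no corresponding figure for alpha subunit.

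**Assumptions.** The log ratio of on-treatment to baseline alpha subunit is taken as normal with mean ln(0.75) = −0.2877 (a 25% fall) and SD s between 0.3 and 0.6. This SD range is assumed.

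**Formulas.**

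- Paired analysis: one-sample t on the log ratio, 18 df, two-sided 5%, noncentrality √19 × 0.2877/s.
- Share crossing the 50% cut: p1 = Φ((ln 0.5 − ln 0.75)/s) = Φ(−0.4055/s).
- Share crossing with no drug effect: p0 = Φ(ln 0.5/s) = Φ(−0.6931/s).
- Exact binomial test of the cut: smallest count whose upper-tail probability under p0 is at most 2.5%.

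| SD of log ratio | Noncentrality | Paired power | p0 | p1 | Expected of 19 | Critical count (actual size) | Power of the cut |
|---|---|---|---|---|---|---|---|
| 0.3 | 4.18 | 98% | 1.0% | 8.8% | 1.7 | 2 (1.6%) | 51% |
| 0.4 | 3.14 | 84% | 4.2% | 15.5% | 3.0 | 4 (0.7%) | 34% |
| 0.5 | 2.51 | 66% | 8.3% | 20.9% | 4.0 | 5 (1.7%) | 36% |
| 0.6 | 2.09 | 51% | 12.4% | 25.0% | 4.7 | 6 (2.3%) | 33% |

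The gap runs from 18 points (SD 0.6) to 50 points (SD 0.4). The binomial test uses less than its nominal 2.5%, so part of the gap is discreteness and not loss of information.

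**What an interval would show.** The 95% half-width on the log scale is 2.101 × s/√19, or 0.145, 0.193, 0.241 and 0.289. Around an observed 25% fall, the interval would be a fall of 13% to 35%, 9% to 38%, 5% to 41%, and about 0% to 44%.

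**Can the planned outputs supply this?**

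- *Normalization.* A 25% fall normalizes only patients starting below 1/0.75 = 1.33 × ULN. Elevated alpha subunit is not an entry criterion (Protocol 5.1 and 5.2).
- *Visit means.* In patients measured at both visits, the difference in means equals the mean change, so the point estimate can be recovered. Its variance is s1² + s2² − 2ρ·s1·s2, and the within-patient correlation ρ is not reported, so the precision cannot.
- *Hormone comparison in Table 31.* It compares V1 testosterone, estradiol, TSH and free T4 by replacement therapy. It does not cover change in alpha subunit.

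**The case against.** The strongest reply is that the objective has already been made operational by two pre-specified endpoints with exact intervals, plus a per-protocol repeat and a subgroup of patients elevated at baseline. The study is a proof of concept with no hypothesis test for alpha subunit, and no document says that a fall of 20% to 30% matters. This stands as a reason to keep both endpoints. It does not explain why the change is estimated for tumor volume and not here.

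Three stronger readings are tempting and should not be drawn:

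- *That alpha subunit is analysed only through the 50% cut, with no within-patient element.* Normalization is a separate endpoint, and the 50% row is itself built from within-patient change. What is missing is a continuous summary of that change.
- *That a fall of 20% to 30% would go undetected.* Nothing is being tested, so the accurate statement is that the fall is not estimated with an interval. The outcome also depends on an unknown SD: at SD 0.5, a 25% fall would put about 4 of 19 patients past the cut.
- *That the SAP tables prove the omission.* The available text shows only a continuation of Table 11, and some footnotes to Tables 11 and B 6 are absent, so rows may be missing. The point therefore rests on the wording of SAP 5.5.1 and Protocol 10.5.1.

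A further reply is that dropout need not distort the visit means much. Protocol 6.4.4 brings patients who stop between Visits 2 and 9 back for the Visit 10 evaluations. That is fair, but it does not restore the missing precision.

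**Conclusion.** The point holds as a modest, low-cost gap. The text plans no continuous within-patient summary of alpha-subunit change and no interval for it, although the objective concerns levels and the same section provides this for tumor volume. In the illustration, the paired analysis does better than the 50% cut at every SD tried, by 18 to 50 points for a 25% fall in 19 patients at two-sided 5%. These figures rest on a log-normal ratio, assumed SDs of 0.3 to 0.6, all 19 patients having both values, and a comparator test that is not in the plan. They show the direction of the gain but do not forecast this trial's results. They also do not carry over to the elevated-at-baseline subgroup, which will be smaller. The pre-specified endpoints are not wrong and need not be demoted.

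**What to change.** In SAP 5.5.1, add one sentence: at each post-baseline visit, the within-patient change in alpha subunit from V1 will be analysed as a log ratio and reported as the geometric mean percent change with a 95% CI, in patients with both values. If the data are skewed or near the assay limit, the median percent change with its CI will also be given. Report this overall and in patients elevated at baseline. Add the matching rows to Tables 11 and B 6, with the sign convention for a reduction stated so that the new rows agree with the 50% row.

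Keep the 50% and normalization endpoints as they are. The cost is a few table rows, with no new samples or visits. The one technical downside is that values near the assay limit need the median or a rank-based version.
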